Side Effects of Atropine (SEA) Study

NCT03593044

November 23, 2021

Research Protocol
Side Effects of Atropine (SEA) Study
Version 1.0

I. Objectives

The purpose of this study is to determine whether there are any changes in subjective or objective measures of eye comfort or vision. Specifically, we will monitor for the following changes:

1. High contrast distance, high contrast near, and low contrast distance visual acuity
2. Pupil size
3. Ability to focus the eyes for near work
4. Reading speed
5. Subjective comfort and vision issues
6. Headaches
7. Intraocular pressure

We hypothesize that pupil size will increase significantly, but no other measures will change clinically meaningfully.

II. Background and Rationale

1.0% atropine is routinely used to dilate pupils and knock out the ability to focus the eyes to see close objects clearly, and it also slows the progression of nearsightedness. Many eye care practitioners are now using 0.01% atropine to slow the progression of nearsightedness because it slows the progression of nearsightedness by 60%¹ to 83%,² and it causes much fewer side effects than 1.0% atropine. One study compared myopia progression and side effects of 0.01%, 0.1%, and 0.5% atropine in children. While 0.5% atropine slowed myopia progression significantly more than 0.01% atropine, there were no other differences in myopia progression over two years, and there were fewer side effects with 0.01% atropine (Table 1), so many eye care practitioners now use 0.01% atropine to slow the progression of nearsightedness.

Table 1. Ocular changes after taking various concentrations of atropine.

	0.01%	0.1%	0.5%	p-value
Accommodative amplitude (D)	-4.6	-10.1	-11.8	<0.001
Pupil size in dim light(mm)	1.15	2.71	3.56	<0.001
Pupil size in bright light (mm)	0.75	2.24	3.11	<0.001
Distance visual acuity (logMAR)	-0.02	+0.01	-0.01	0.44
Near visual acuity (logMAR)	-0.02	+0.06	+0.25	<0.001
Asked for glasses to improve near vision (% yes)	6	61	70	<0.001

Another study examined the changes in visual function and symptoms of young adults while taking daily drops of 0.01% atropine for five days. Only pupil size and pupil response exhibited a significant change over that time period (Table 2).

Table 2. The change in vision function while taking 0.01% atropine for five days.

	Day 1	Day 3	Day 5	p-value
Distance VA (logMAR, OD)	-0.10 ± 0.10	-0.08 ± 0.07	-0.08 ± 0.05	0.55
Near point of accommodation (D)	10.2 ± 1.42	10.0 ± 1.39	9.1 ± 2.12	0.08
Pupil size (mm, OD)	5.51 ± 1.74	6.55 ± 1.12	6.82 ± 0.61	0.04
Pupil response	3.0 ± 0.0	2.8 ± 0.5	1.1 ± 0.9	<0.01
Reading speed (words per second)	3.36 ± 0.55	3.16 ± 0.54	3.25 ± 0.45	0.12
Near point of convergence (cm)	6.8 ± 2.4	7.0 ± 2.2	8.0 ± 3.2	0.25

We plan to examine a wider range of objective measures of visual function and symptoms than previous investigations, including investigate the changes in vision, pupil size, the ability to focus the eyes for near work, reading speed, comfort of the drops, subjective visual effects, presence and severity of headaches, and whether or not someone would be willing to take the drops long-term if they delayed the onset of nearsightedness.

III. Procedures

A. Research Design

This is a prospective cohort study in which we will compare pre-treatment measures to post-treatment measures after taking the treatment for approximately one week. The subjects will serve as their own controls. This will allow us to see the changes to be expected while taking the eye drop. Because the half-life of the drug is approximately 4 hours and maximum cycloplegia (eyes can't focus for near work) occurs in less than one hour, a longer period of time is not required.

B. Sample

We will examine adults between the ages of 21 and 30 years. We are not examining the effects in children because adults will give a more accurate description of the side effects they experience than children. Because children typically complain less about eye comfort and vision issues than adults,³ we strongly believe that we will obtain data that would be considered the worst case scenario for children. The specific entry criteria are listed in Table 3.

Table 3. Entry criteria

Age	21 to 30 years, inclusive
Accommodation	No known history of accommodative issues or therapy

All subjects in the age range specified with no known accommodative (focusing) issues will undergo consent and be enrolled.

Most of this experiment is hypothesis generating, but we can estimate a sample size based on a two measures, assuming $\alpha = 0.05$ and power = 80%. We aim to detect a change in pupil size of 1.0 mm because this is approximately what was reported in previous studies and what may begin to be clinically meaningful. We conservatively estimate a SD of change of 1.0. We also aim to detect a change in visual acuity of 0.1 logMAR, which is one line of visual acuity, a clinically meaningful change, with a standard deviation change of 0.2. The sample size required for pupil size is eight subjects and the sample size for visual acuity is 31 subjects. We will aim to enroll a sample sufficient to detect both the pupil size and visual acuity change. Assuming a 10% drop out rate, we estimate a sample size of 35, and we include five extra subjects who may be ineligible, for a total sample size of 40 subjects.

C. Measurement / Instrumentation

Manifest Refraction

This is a standard clinical procedure used to measure glasses prescriptions during clinical examinations. Cycloplegic autorefraction, the standard measure of eye prescription in many studies, is not necessary because we are not measuring the change in prescription over time.

Phoria

We will measure phoria at near in order to determine whether low concentration atropine affects how the two eyes work together. Modified Thorington is a more repeatable and less subjective method of measuring phoria than alternating cover test.

Visual Acuity

We will measure the high contrast (black letters) visual acuity at distance and near and the low contrast (grey letters) at distance using logMAR visual acuity charts and scoring on a letter basis. These measures of vision are standard protocols for vision research.

We will measure the pupil size with the NeuroOptics VIP-200 Pupillometer (NeuroOptics, Inc., Irvine, CA) in bright and dim light. For the dim light condition, the subject will stand with his or her back toward the wall-mounted visual acuity chart with the room lights off except for the incandescent lamp pointed straight down over the examination chair at the opposite end of the room. For the bright condition, the subject will stand with his or her back toward the wall-mounted visual acuity chart, and the visual acuity chart illumination should be turned on and be the same as when taking visual acuity measurements (approximately 75 – 120 cd/m² or 9.3-9.9 EV).

A detailed target on a stick will be too near the eyes to read the letter. The stick will be pulled away from the subject until the subject reads the letter. The distance between the forehead and the stick will be measured to determine the ability to focus.

While wearing full vision correction, the prescription will be measured ten times while looking at distance target using the Grand Seiko WAM-5500 Binocular Autorefractor/Keratometer (AIT Industries, Bensenville, IL). A target will then be placed at 33 cm, and the subject will be told to keep the target clear while measuring the prescription five times. The prescription at distance will be subtracted from the prescription at near, and that result will be subtracted from 3.0 D, which is the focusing demand.

Reading Speed will be measured using the Rate of Reading Test. This test contains the same 15 simple words, repeated on each line and presented in random order. It is meant to serve as a test of reading speed pre- and post-intervention.

Subjects will view a card held at 40 cm. Flippers with +2.50 D lenses on one side and -2.50 D lenses on the other side will be placed in front of the subject, and the subject will report when the letters become clear. The lenses will be flipped, and the subject will again report when the print is clear. This will be continued for 1 minute, and the number of flips will be counted. This is a routine clinical measure of the ability to change focus from distance to near.

We will survey subjects about light sensitivity, drop comfort, likelihood of taking the drop to delay the onset of nearsightedness, vision symptoms, headaches, and comfort of the proparacaine eye drop and an artificial tear eye drop (for comparison of drop comfort to low concentration atropine). We will use the following format to collect survey data (using different questions and anchors as necessary):

1	2	3	4	5	6	7	8	9	10
Good									Perfect

We will measure the pressure in the eye using a Tonopen, a clinical measure that is performed during routine eye examinations. This requires a drop of 1% proparacaine in each eye to numb the eye. This drop is also used during routine eye examinations.

D. Detailed Study Procedures

Manifest Refraction

The examiner will measure glasses or perform retinoscopy to get a starting point for the refraction. The refraction will be performed using Jackson crossed cylinder, binocular blur balance, and maximum-plus-to-maximum-acuity to obtain the final refraction.

Phoria

The subject holds the Maddox rod horizontally in front of the right eye for 30 seconds before testing. Hold the near Muscle Imbalance Measure (MIM) card 40cm from the subject. Encourage the subject to keep the letters and numbers on the card clear, and shine the penlight through the hole in the center of the card. Ask the subject whether the red line is on the side of the red triangle (esophoria) or the blue circle (exophoria), and have the subject to tell you the number the line goes through. The card is marked with even numbers only, so if the subject states that the line is between two numbers, record the number between them (for example, if the line is between the 2 and the 4 on the red triangle side of the card, record 3pd esophoria). Record the finding using a positive sign (+) to indicate **eso** deviations and a negative sign (–) to indicate **exo** deviations.

Visual Acuity

Bailey-Lovie logMAR charts will be calibrated to 9.3 to 9.9 EV (75 to 120 cd/m²). The subject stands 4 meters from the chart and reads the first letter on each line, continuing down the chart until the first letter is missed. She starts two lines above the missed letter and reads five letters from every line. If she misses a letter on the first line, she continues up the chart until she reads all five letters correctly. She must guess five letters on each line until three or more letters is missed in a single line. If she gets 3 or more correct on the bottom line, move to 6 meters and repeat. If she does not get all five letters correct on the top line, move the subject to 2 meters and repeat. The total number of letters read correctly and the final test distance are recorded for each visual acuity measurement.

Pupil Size

Press the OD button to activate the unit. Bring the unit up in front of the subject's right eye with the eye cup resting against the subject's face and hold down the OD button continuously. When the pupil is marked with a green circle, release the button to initiate the measurement. Hold the unit still during the few seconds of the measurement. Take care that the eyelids do not cover the pupil. If the green measurement circle was not centered over the pupil, delete the measurement by using the Eraser icon at the right side of the three-icon Tool menu. Repeat the measurement until the green measurement circle is centered over the pupil. Record the pupil size to the nearest 0.1 millimeter on the examination form. Repeat steps 6-9 while the lights are in the mesopic condition.

Focusing Ability

A letter target on a stick is placed against the nose, in front of the eyes. Tell the subject the stick will be moved slowly away until the subject can first read the letter correctly. The subject should say the letter as soon as s/he can read it. The distance from the forehead to the stick is measured to the nearest cm and recorded.

Lag of Focus

Place the manifest correction used for visual acuity in a trial frame, minimizing the number of lenses used in the trial frame. Place an occluding trial lens in the trial frame well over the left eye so that the subject will only view targets with the right eye. Place the 33cm near rod in the central slot to measure accommodative lag in primary gaze only. Place the subject's chin on the chinrest and forehead against the forehead rest. Obtain a view of the eye on the screen. The white keratometry circle should be in focus. Centered the pink reticule within the white keratometry ring. Encourage the subject to keep the letters as clear as possible throughout the measurement and have the subject focus on a specific letter to ensure the subject is attentive and accommodating. Obtain at least five readings without the "retry" message. When in doubt, take additional measurements to ensure that at least 5 measurements exist. Press Print and tape the printout in the location indicated on the exam form.

Reading Speed

Tell the subject you want him/her to read the random words on a page as quickly as possible without making any mistakes. If you make a mistake, just continue reading the card. You will read for one minute. I will tell you when to start and when to stop. Have the subject hold Test A at 40 cm. Tell the subject to begin and immediately begin the stop watch. Put a line through each mistake. Circle the last word read correctly and record the number of words read correctly. If more than five mistakes occurred, have the subject read for another minute and continue until the subject makes five or fewer mistakes.

Ability to Shift Focus

Subjects hold the near visual acuity card at 40 cm. Flippers with +2.00 D lenses on one side and –2.00 D lenses on the other side will be placed above the subject's eyes. Tell the subject to say "now" as soon as the letters on the card are clear after each flip of the lenses. This will be timed for one minute, and the number of cycles will be recorded. Begin with the +2.00 D lenses and measure binocularly.

Surveys

Subjects will be told to circle the number that corresponds to their perception that answers each question, noting the descriptions at each end of the numbers.

Pressure in the Eye

Place one drop of 1.0% proparacaine in each eye of the subject, and have him/her answer the three questions about eye comfort after receiving the drop. Place a sheath on the measurement tip of the Tonopen. Have the subject view a distant object while holding the eye open. Press the button on the Tonopen and wait until the green light turns on. Lightly tap the Tonopen on the cornea, until a final "beep" sounds. If the screen has a "95" in the bottom right corner, then the measure is valid and can be recorded. If anything else is displayed, repeat the procedure.

Compounding of the 0.01% Atropine

The drug will be compounded by the Central Ohio Compounding Pharmacy. They will dissolve 0.1 g atropine sulfate USP monohydrate powder in 1000 mL sterile water to a final concentration of 0.01%, and add Benzalkonium Chloride as preservative.

E. Internal Validity

We will measure the potential side effects of low concentration atropine in adults rather than children, although children will ultimately receive low concentration atropine for myopia control. We are not examining the effects in children because adults will give a more accurate description of the side effects they experience than children. Because children typically complain less about eye comfort and vision issues than adults,³ we strongly believe that we will obtain data that would be considered the worst case scenario for children.

We will use a pre- post-test format in order to examine the changes to be expected over a short period of time. The first week of experience will typically guide the likelihood of long-term commitment to the treatment.^{4,5} We therefore want to know how much administration of low concentration atropine will have on subjects' vision.

F. Data Analysis

We will perform repeated measures t-tests to determine whether there are significant changes over time for normally distributed variables and Wilcoxon signed-rank tests to determine whether there are significant changes over time for non-normally distributed variables.

IV. Bibliography

4. Lang JM. The use of a run-in to enhance compliance. *Stat Med*. 1990;9(1-2):87-93; discussion 93-85.

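### The hypothesis of no clinically meaningful change outside pupil size is paired only with tests of zero change, which cannot support or refute it

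*Combined protocol and SAP*

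**What the plan says.** Section I gives the purpose as finding out whether any measure of eye comfort or vision changes, lists seven domains to monitor, and then states one hypothesis: "We hypothesize that pupil size will increase significantly, but no other measures will change clinically meaningfully". The sentence separates statistical significance, expected for pupil size, from clinical meaning, which is denied for everything else.

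Section III.F is the entire analysis plan: "We will perform repeated measures t-tests to determine whether there are significant changes over time for normally distributed variables". Where a variable is not normal, the signed-rank test takes the place of the t-test. The section gives no margin, no confidence-interval rule, no equivalence or non-inferiority test, and no rule for reading a non-significant result.

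Outside pupil size, section III.B sets a meaningful size for one measure only: "We also aim to detect a change in visual acuity of 0.1 logMAR, which is one line of visual acuity, a clinically meaningful change". It uses that figure to power a difference test. It gives no such figure for focusing ability, reading speed, comfort, headaches or intraocular pressure. The same section describes most of the experiment as hypothesis generating.

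**The concern.** For six of the seven domains the hypothesis is that a meaningful change is absent. Failing to reject zero change does not show this, because the data may still be compatible with a change larger than the meaningful size. Rejecting zero does not refute it either, because the change may be trivial. The plan has the yardstick for acuity but never compares the result with it.

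The background shows how easily the two can be run together. It summarises the five-day study in young adults by saying that only pupil size and pupil response changed significantly. In Table 2 of that study the near point of accommodation falls from 10.2 D on day 1 to 9.1 D on day 5, with p = 0.08. For focusing ability the present plan offers neither a threshold nor a power statement with which to interpret a result of that kind. Sections III.B and III.E also present the adult data as a worst case for children, so an unsupported reassurance could carry over to them.

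**Working it through.** **Inputs.** From III.B: two-sided α 0.05 (the sidedness is not stated, but two-sided reproduces both figures), power 80%; pupil size change 1.0 mm, SD of change 1.0; acuity change 0.1 logMAR, SD of change 0.2; 10% dropout; five extra subjects. From Table 2: distance acuity SD 0.10 on day 1 and 0.05 on day 5, means -0.10 and -0.08 logMAR.

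**1. The plan's own sample size.** n = (SD × (1.960 + 0.842) / δ)².
- Pupil size: (1.0 × 2.802 / 1.0)² = 7.85, so 8.
- Acuity: (0.2 × 2.802 / 0.1)² = 31.4, stated as 31.
- Dropout: 31 / 0.9 = 34.4, so 35; plus 5 gives 40.

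All stated figures reproduce.

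**2. What a non-significant acuity result excludes at SD 0.2, n = 31.** The largest non-significant mean is t(0.975, 30) × SD / √n = 2.042 × 0.2 / √31 = 0.073 logMAR. Its upper 95% limit is twice that, 0.147, or about one and a half lines. With 35 evaluable the figures are 0.069 and 0.137. A true loss of exactly 0.1 logMAR gives a non-significant paired t-test 23% of the time with 31 and 18% with 35.

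**3. How this depends on the SD.** Every non-significant result excludes 0.1 logMAR when 2 × 2.042 × SD / √31 < 0.1, that is, when the SD is below 0.136. Table 2 gives no SD of change, so a correlation between days must be assumed:
- correlation 0: √(0.10² + 0.05²) = 0.112
- correlation 0.5: √(0.10² + 0.05² - 2 × 0.5 × 0.10 × 0.05) = 0.087

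| SD of change | Largest non-significant mean (logMAR) | Its upper 95% limit (logMAR) |
|---|---|---|
| 0.2 (plan) | 0.073 | 0.147 |
| 0.112 | 0.041 | 0.082 |
| 0.087 | 0.032 | 0.064 |

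At the Table 2 values, false reassurance on acuity does not arise. The error then runs the other way: a shift of 0.03 to 0.04 logMAR, under half a line, is already significant.

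**4. Whether a margin rule is workable.** Conclude no meaningful change if the 90% interval of the mean paired change lies within ±0.1 logMAR. This is two one-sided tests at 0.05 each. At SD 0.2 and n = 31 the half-width is 1.697 × 0.2 / √31 = 0.061. Power by simulation with t-based intervals:

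| Evaluable | SD | True change (logMAR) | Power |
|---|---|---|---|
| 31 | 0.2 | 0 | 72% |
| 35 | 0.2 | 0 | 79% |
| 36 | 0.2 | 0 | 81% |
| 31 | 0.2 | 0.02 | 65% |
| 36 | 0.2 | 0.02 | 73% |
| 31 | 0.112 | 0 | over 99% |

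A shift of 0.02 is the difference between the day 1 and day 5 means in Table 2. Having 36 evaluable requires 40 enrolled, 10% dropout (40 × 0.9 = 36) and none of the five extra subjects proving ineligible.

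**5. Other measures.** No corresponding figures can be computed, because the documents give no meaningful threshold for them.

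**The case against.** The stated purpose is to find out whether anything changes, and section III.B is framed in terms of detection. Difference tests serve that purpose and the pupil size hypothesis. This stands: the gap concerns one part of the hypothesis, and it would be wrong to infer that the analysis fails the study as a whole.

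A reader might also infer that the investigators will treat non-significance as proof of no change. No passage says so. The supportable statement is that III.F offers no other means of judging that part of the hypothesis, so the misreading is possible.

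Acuity has a stated threshold and nominal 80% power to detect it. That softens the problem for acuity, although power before the study does not say what a particular non-significant result excludes. It does not help the measures without a threshold or power statement.

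The two acuity risks depend on different SDs. At SD 0.2 only observed shifts above 0.073 logMAR are significant, which is not trivial; at the SDs derived from Table 2, a non-significant result is truly reassuring. They should not be presented as holding together.

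Lastly, a study that is mostly hypothesis generating need not be held to a confirmatory equivalence standard. This lowers the severity, but a stated hypothesis still needs an analysis that bears on it.

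**Conclusion.** The point holds as something that should be fixed. As written, III.F cannot support or refute the claim of no clinically meaningful change outside pupil size. For acuity at SD 0.2 and 31 evaluable, a non-significant result is compatible with a loss of up to 0.147 logMAR, against the plan's 0.1. Below an SD of about 0.136 the concern shifts to small changes that are significant but not meaningful, namely 0.03 to 0.04 logMAR at SD 0.087 to 0.112. That range rests on an assumed correlation of 0.5 to 0. The gap is widest for focusing ability, reading speed, comfort, headaches and intraocular pressure.

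A reader might conclude that a formal equivalence test is fully powered at the planned size. The plan's own SD does not support this: power is 72% with 31 evaluable and passes 80% only at 36, with a true change of exactly zero.

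**What to change.** In III.F:
- Keep the difference tests, including the one for pupil size.
- Report every change with a confidence interval. For variables assigned to the Wilcoxon test, use an interval for the median change or the Hodges-Lehmann estimate.
- For each of the three acuity measures (high contrast distance, high contrast near, low contrast distance), conclude no clinically meaningful change only if the 90% interval of the mean paired change lies within ±0.1 logMAR.
- For any other measure, make that claim only against a margin that the investigator sets before analysis. Where none is set, report the estimate and its 95% interval without the claim.

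The cost is a few sentences and a short table of margins, with no new subjects or data. The downside is that some measures will end as inconclusive. At SD 0.2 and no true change, this would happen for a given acuity measure in about 28% of studies with 31 evaluable subjects (100% - 72%).

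### Entry criteria neither exclude, defer nor record atropine or other dilating or focus-relaxing drops, so some baselines may be drug-affected and the pupil and focusing changes underestimated

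*Combined protocol and SAP*

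**What the plan says.** Section III.B refers the reader to Table 3 for the specific entry criteria. Table 3 has two rows: age, "21 to 30 years, inclusive", and accommodation, "No known history of accommodative issues or therapy". The sentence after the table reads "All subjects in the age range specified with no known accommodative (focusing) issues will undergo consent and be enrolled".

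Section III.A describes a single-group comparison of measures before and after about one week of drops: "The subjects will serve as their own controls". Section III.F analyses the change with a paired t-test or a Wilcoxon signed-rank test. Section I expects a larger pupil and no clinically meaningful change in anything else, which includes focusing.

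On the drug class, Section II says "1.0% atropine is routinely used to dilate pupils and knock out the ability to focus the eyes to see close objects clearly" and adds that many practitioners now prescribe the 0.01% strength. On duration of action, Section III.A argues for a short study "Because the half-life of the drug is approximately 4 hours and maximum cycloplegia (eyes can't focus for near work) occurs in less than one hour".

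No section excludes users of atropine or of other dilating or cycloplegic drops, sets a drop-free interval before baseline, or asks about eye drops or medication at either visit.

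**The concern.** In a controlled trial, a few drug-affected baselines would be spread over both arms. Here the baseline is the only control, so an earlier drug effect enters the result directly and nothing in the design would reveal it.

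Two kinds of subject matter. One was dilated shortly before baseline and has recovered by the second visit: that pupil may shrink and focusing may improve while on study drug. The other already uses atropine or a similar drop: pupil and focusing have already moved, and little further change is left to see. Both make the study drug look milder than it is.

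For pupil size this works against the investigators' hypothesis. For focusing it works in favour of it, which is the uncomfortable direction in a study of side effects. Focusing also has no sample-size calculation, so nothing in the plan shows how much dilution that comparison could bear.

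**Working it through.** **1. The plan's own sample size (Section III.B).** Inputs: two-sided α of 0.05 (sidedness is not stated, but two-sided reproduces the figures), power 80%, pupil change 1.0 mm with SD of change 1.0, visual acuity change 0.1 logMAR with SD of change 0.2.

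n = (1.960 + 0.842)² × (SD/Δ)² = 7.85 × (SD/Δ)²

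- Pupil: 7.85 × 1 = 7.85, so 8, as stated.
- Acuity: 7.85 × 4 = 31.4, so 31 to the nearest whole number, as stated (32 if rounded up).
- Dropout: 31/0.9 = 34.4, so 35; adding five gives 40, as stated.

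The study is therefore sized by acuity, and pupil size has far more subjects than its own calculation asks for.

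**2. Model for an affected baseline.** Let a fraction f of subjects have a change that is d smaller than that of the others. Then:

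- mean change = Δ − f·d
- SD of change = √(σ² + f(1 − f)d²)

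Power is from the two-sided paired t-test at 31 subjects, using this mean and SD. The documents give no value for f. I show 1 of 35 (f = 0.0286) and 3 of 35 (f = 0.0857) as assumptions.

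**3. Pupil, Δ = 1.0 mm, σ = 1.0.** Assume d = 2.24 mm (Table 1, bright light, 0.1% atropine), with the effect gone by the second visit.

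| Affected | Bias f·d | Mean change | Added variance | SD | Power |
|---|---|---|---|---|---|
| 0 | 0 | 1.00 mm | 0 | 1.00 | >99% |
| 1 of 35 | 0.06 mm | 0.94 mm | 0.14 | 1.07 | >99% |
| 3 of 35 | 0.19 mm | 0.81 mm | 0.39 | 1.18 | 96% |

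If affected subjects simply show no change (d = 1.0 mm), 10% affected gives a mean of 0.90 mm and power above 99%.

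A harsher case takes Table 1's dim-light figures and lets affected pupils shrink by 3.56 − 1.15 = 2.41 mm, so d = 3.41 mm. The mean is then 0.83, 0.66 and 0.32 mm at 5%, 10% and 20% affected, with power 95%, 70% and 17%. Real masking of the pupil change needs roughly a tenth of subjects or more to arrive strongly dilated.

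**4. Focusing.** Assume a true fall of 10.2 − 9.1 = 1.1 D (Table 2, Day 1 to Day 5) and σ between 1.5 and 2.5 D; Table 2 gives no SD of change. Assume d = 4.6 D (Table 1, 0.01% atropine), gone by the second visit.

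| Affected | Bias f·d | Mean fall | SD | Power |
|---|---|---|---|---|
| 0 | 0 | 1.10 D | 1.50–2.50 | 98%–66% |
| 1 of 35 | 0.13 D | 0.97 D | 1.68–2.61 | 87%–51% |
| 3 of 35 | 0.39 D | 0.71 D | 1.98–2.81 | 49%–27% |

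If affected subjects simply show no change (d = 1.1 D), 10% affected gives a mean fall of 0.99 D and power 94%–56%.

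**5. How long an earlier drop matters.** With the stated half-life of about 4 hours, the fraction left is 0.5^(12/4) = 12.5% at 12 hours, 0.5^(24/4) = 1.6% at 24 hours and 0.02% at 48 hours. Yet in Table 2, under daily drops, pupil size runs 5.51, 6.55, 6.82 mm and pupil response 3.0, 2.8, 1.1 over Days 1, 3 and 5. Continued change to Day 5 sits uneasily with an effect that clears within a day. It is not direct evidence on recovery, so the documents do not settle the duration.

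**The case against.** The strongest reply is that the gap may never matter in practice. Nothing suggests that adults of 21 to 30 would often be on atropine; the use described is myopia control in children. The protocol calls its baseline pre-treatment, rules out accommodative therapy, budgets for ineligible recruits, and regards most of its aims as exploratory. On its half-life figure, carry-over is confined to about the previous day. All of this lowers the likely number affected. None of it closes the gap: the half-life does not help with current users or a very recent dilation, therapy in the accommodation row does not clearly cover myopia drops or diagnostic dilation, and the allowance for ineligible recruits comes with no further eligibility rule.

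Three stronger readings are tempting and not supported.

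- A reader might infer that the pupil change would be hidden. With a small share affected it is diluted, and power remains high because acuity sets the sample size.
- A reader might infer that the bias always runs towards no side effect. A drug effect equally present at both visits largely cancels, unless it leaves little room for further change, and a drug started during the study week would push the other way.
- A reader might take Table 1's 10.1 D loss as the likely shift in an affected subject. It was measured in children on 0.1% atropine and nearly equals the whole 10.2 D of Table 2's young adults on Day 1. The 2.24 mm and 4.6 D used above also come from children and are illustrations only.

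**Conclusion.** The gap is real and lies in the operative entry rule: as written, it admits people whose baseline may already be drug-affected, and it leaves no record by which to find them. The likely consequence is an underestimated size of change and a weaker focusing comparison, not a failure to detect pupil dilation. With 3 of 35 affected under the 2.24 mm assumption, the pupil change is understated by 0.19 mm and power is about 96%. For focusing, one affected subject in 35 with a 4.6 D shift understates a 1.1 D fall by 0.13 D and lowers power from 98%–66% to 87%–51%.

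These figures rest on an assumed number affected, shifts taken from children, an assumed SD of change for focusing, and full recovery by the second visit. The number affected may be zero. The change is worth making because it is cheap and the design has no other safeguard.

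**What to change.** - Add to Table 3 an exclusion for current users of atropine or of other dilating or cycloplegic drops.
- Add a deferral for anyone given such a drop within a stated drop-free interval before baseline. The investigators should set its length and, in doing so, reconcile the 4-hour half-life in Section III.A with Table 2's changes continuing to Day 5. The documents support no particular number of days.
- Reword the enrolment sentence after Table 3 to match.
- Record eye-drop use and relevant medication at both visits, and add to Section III.F a sensitivity analysis without the subjects so identified.

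The cost is some protocol wording, a short history at each visit, and a few deferred or excluded volunteers. The five extra places already budgeted can absorb these, and the sample-size figures of 8, 31, 35 and 40 do not change.
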